4.4. Coding Dictionaries

Medical history and AEs will be coded using the Medical Dictionary for Regulatory Activities (MedDRA, version 26.0). Prior and concomitant medications will be coded using the World Health Organization (WHO) Drug Dictionary (March 2020 B3 Global version).

5. STUDY POPULATION

5.1. Disposition

The summary of subject enrollment and disposition will include:

- The total number of subjects who provided informed consent
- The following categories will be presented. The number of subjects enrolled will serve as the denominator to calculate percentages.
 - Enrolled subjects
 - Direct enrollment by CSWS2010 treatment assignment: subjects who directly rolled over from CSWS2010
 - Non-direct enrollment by CSWS2010 treatment assignment: subjects who enrolled after a gap following completion of CSWS2010
 - De novo enrollment: subjects who did not participate in CSWS2010
 - Completed study drug dosing
 - Discontinued study drug dosing, including reasons
 - Completed study
 - Last Long-Term Treatment Period completed: Schedule A
 - Last Long-Term Treatment Period completed: Schedule B
 - Last Long-Term Treatment Period completed: Schedule C
 - Discontinued study, including reasons
 - Discontinued in Schedule A
 - Discontinued in Schedule B
 - Discontinued in Schedule C

A listing will be provided which includes subject identification (ID), the date of informed consent, the date of enrollment, CSWS2010 treatment assignment, and the dose at Day 1 of CSWS2025.

5.2. Summary of Analysis Sets

A summary of the number and percentage of subjects included in (and excluded from, as applicable) each analysis set will be provided.

5.3. Protocol Deviations

Protocol deviations will be reviewed and tracked as described in the study-specific Protocol Deviation Plan. Prior to database lock, all major protocol deviations will be exported to a file and integrated into the study data.

Neurocrine Biosciences, Inc.
Statistical Analysis Plan

Study NBI-827104-CSWS2025
6 September 2024

Prior to database lock, the study team will review a listing of all major protocol deviations and determine which deviations are IPDs. IPDs are protocol deviations that might significantly affect the completeness, accuracy and/or reliability of the study data or that might significantly affect a subject's rights, safety, or well-being.

A summary of the number and percentage of all enrolled subjects with IPDs by deviation category will be presented. The summary will be repeated for the subset of IPDs that are related to the coronavirus disease 2019 (COVID-19) pandemic (if applicable).

All major protocol deviations will be presented in a data listing and any that are classified as IPDs will be flagged in the listing. Any major protocol deviations related to the COVID-19 pandemic (if applicable) will also be flagged in the listing.

5.4. Demographic and Baseline Characteristics

Demographics and study baseline characteristics will be summarized descriptively for all enrolled subjects. Baseline is defined according to Section 4.3.1.

The following variables will be summarized:

- Demographics: age, age groups [REDACTED], sex, ethnicity, race, country
- Baseline subject characteristics: height [cm], weight [kg], body mass index [BMI, kg/m²], Tanner stage [stage 1, 2, 3, 4, or 5]
- Baseline [REDACTED]
- Baseline [REDACTED]
- Medications: number of concomitant ASMs at baseline, number of prior ASMs, rescue medications at baseline [yes/no], non-drug antiseizure treatments at baseline [yes/no]

5.5. Medical History

Medical history information was entered into the CSWS2025 database by site staff. For subjects that participated in CSWS2010, this included the subject's medical history reported in CSWS2010 as well as any AEs from that study that were ongoing at the time of enrollment into CSWS2025. Medical history will be summarized descriptively for all enrolled subjects. Medical history data will be coded using MedDRA. Data will be summarized with frequencies and percentages of subjects with at least one medical history item, and subject frequencies and percentages according to the system organ class (SOC) and preferred term (PT) levels. The table will be sorted alphabetically by SOC and then, within an SOC, by PT.

Neurocrine Biosciences, Inc.
Statistical Analysis Plan

Study NBI-827104-CSWS2025
6 September 2024

6. IMPACT OF COVID-19 PANDEMIC

This section describes analyses and summaries that will be produced to help determine the potential impact of the COVID-19 pandemic on the study conduct/data and additional details regarding how data that is potentially impacted by the COVID-19 pandemic will be handled in the analysis plan. It is in alignment with the guidance put forth by the US Food and Drug Administration (FDA; Considerations for the Conduct of Clinical Trials of Medical Products During Major Disruptions Due to Disasters and Public Health Emergencies [March 2020, updated September 2023]) and European Medicines Agency (EMA; Points to consider on implications of Coronavirus disease [COVID-19] on methodological aspects of ongoing clinical trials [March 2020]).

To help understand the impact of the COVID-19 pandemic on the clinical trial data, the following listings will be generated:

- A listing of all subjects affected by the COVID-19 pandemic. The listing will identify subjects who experience at least one of the following situations due to the COVID-19 pandemic (additional situations may be included):
 - Discontinued study due to COVID-19
 - Presumed or confirmed diagnosis of COVID-19
 - Had at least one COVID-19 pandemic-related major protocol deviation
 - Missed at least one study visit due to COVID-19
 - Missed at least one assessment due to COVID-19
 - Required at least one assessment to be collected using a method other than what is defined in the protocol (eg, remotely) due to COVID-19
- A listing of subjects who withdrew from study due to the COVID-19 pandemic, which will include the specific reasons.
- A listing by subject of visits and assessments affected by the COVID-19 pandemic (eg, missing, partial, collected remotely).

The above listings may be omitted if it is known there was no impact of the COVID-19 pandemic on the study conduct.

The broad Standardized MedDRA Query (SMQ) of COVID-19 will be utilized to identify PTs pertaining to subjects with a presumed or confirmed diagnosis of COVID-19 (using MedDRA version 26.0).

Further classification and summaries of major protocol deviations related to the COVID-19 pandemic are detailed in Section 5.3.

Neurocrine Biosciences, Inc.
Statistical Analysis Plan

Study NBI-827104-CSWS2025
6 September 2024

7. **EFFICACY**

The efficacy endpoint and planned analysis methods are described below. Efficacy analyses will be based on the full analysis set. [REDACTED]

[REDACTED]

[REDACTED]

7.1. [REDACTED]

[REDACTED]

[REDACTED]

[REDACTED]

Neurocrine Biosciences, Inc.
Statistical Analysis Plan

Study NBI-827104-CSWS2025
6 September 2024

8. [REDACTED]

8.1. [REDACTED]

[REDACTED]

[REDACTED]

[REDACTED]

[REDACTED]

[REDACTED]

[REDACTED]

[REDACTED]

[REDACTED]

[REDACTED]

[REDACTED]

[REDACTED]

[REDACTED]

[REDACTED]

[REDACTED]

[REDACTED]

[REDACTED]

8.2. [REDACTED]

[REDACTED]

[REDACTED]

[REDACTED]

- I [REDACTED]
- I [REDACTED]
- I [REDACTED]
- I [REDACTED]
- I [REDACTED]
- I [REDACTED]
- I [REDACTED]
- I [REDACTED]
- I [REDACTED]

[REDACTED]

[REDACTED]

[REDACTED]

[REDACTED]

[REDACTED]

[REDACTED]

[REDACTED]

[REDACTED]

[REDACTED]

[REDACTED]

[REDACTED]

9. SAFETY

The safety objective of the study is to characterize the safety profile of NBI-827104 as measured by treatment-emergent adverse events (TEAEs) and serious adverse events (SAEs), clinical laboratory tests, body weight, neurological and [REDACTED] examinations, vital signs, electrocardiogram (ECG), Columbia-Suicide Severity Rating Scale (C-SSRS), Tanner Stage, and medications. All outputs for safety endpoints will be based on the safety analysis set. The analysis of the safety data will be based on descriptive statistics and presented according to the nominal study visit unless otherwise noted. Safety data will not be subject to any imputation and will be summarized on an observed case basis. No formal hypothesis-testing analysis of safety data will be performed.

9.1. Study Drug Dosing and Compliance

The duration of exposure to study drug will be calculated as: last dose date – first dose date +1. Duration of exposure will be summarized with descriptive statistics by dose and for all subjects.

A summary of dose received will be presented by visit.

The site will enter into the eCRF whether the subject's dosing compliance since the previous visit was <50%, 50%-<80%, 80%-<90%, 90%-100%, >100%-120%, >120%, or Not Done. The number and percentage of subjects who have a dosing compliance of <80%, 80%-120%, >120%, and Not Done will be presented for each postbaseline visit.

A listing of the lot numbers will be summarized for all enrolled subjects.

9.2. Adverse Events

A TEAE is an AE not present prior to the initiation of study drug dosing in CSWS2025, or is an already present condition that worsens either in intensity or frequency following the initiation of study drug dosing in CSWS2025. It is defined by an onset date and time on or after the date of the first dose and within the 14 days after the date of the last dose. If the AE onset date and time are unknown, it will be assumed that the AE is a TEAE. If the AE onset time is unknown but the AE onset date is the same date as the first dose of study drug, it will be assumed that the AE is a TEAE. See details for imputing missing/partial start dates (Section 4.3.5.1). There will be no imputation for AE stop dates.

TEAEs, categorized by MedDRA SOC and/or PT, will be summarized in frequency tables. The frequency tables will include the number and percentage of unique subjects experiencing each event at least once during the study.

An overall summary table will be provided which summarizes the number and percentage of unique subjects with any TEAE, treatment-emergent SAE, TEAE leading to study drug dose reduction but not study drug discontinuation, TEAE leading to study drug interruption but not study drug discontinuation, TEAE leading to study drug discontinuation, TEAE leading to study discontinuation, and TEAE resulting in death. The summary table will also include the frequency distribution of the maximum TEAE intensity (mild, moderate, severe) reported for each subject.

The following summary tabulations will also be presented. Unless otherwise noted, the tables will be sorted in alphabetical order. The first line of the table will display the number and percentage of subjects with at least one of the following TEAE categories:

- TEAEs, classified by SOC and PT
- TEAEs, classified by PT, displayed in a descending order by frequency
- Treatment-emergent SAEs by SOC and PT
- TEAEs leading to study drug dose reduction, not leading to discontinuation by SOC and PT
- TEAEs leading to study drug interruptions, not leading to discontinuation by SOC and PT
- TEAEs leading to study drug discontinuation by SOC and PT
- TEAEs leading to study discontinuation by SOC and PT
- TEAEs leading to death by SOC and PT

A listing of TEAEs resulting in study drug discontinuation will be provided which includes subject ID, the dose being received at the onset time of the TEAEs leading to study drug discontinuation, study day of the discontinuation, and other relevant information from the AE eCRF.

Separate listings of SAEs, fatal AEs, and TEAEs resulting in study drug dose reductions will also be provided. In the event that no subjects experience SAEs, fatal AEs, or TEAEs resulting in study drug dose reductions, the blank listing shell will be presented with text printed in the center of the listing describing that no adverse events of that type occurred during this study.

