10.1. Definition

An AE is any untoward medical occurrence in a patient or clinical investigation subject administered a pharmaceutical product that occurs after enrollment into the study and which does not necessarily have a causal relationship with the study treatment. An AE can therefore be any unfavorable and unintended sign (including an abnormal laboratory finding, for example), symptom, or disease temporally associated with the use of a medicinal product, whether or not considered related to the medicinal product.

A treatment-emergent adverse event (TEAE) is an AE that started or worsened in severity following the first dose of study treatment.

Adverse events include, but are not limited to, any of the following:

- Worsening or change in nature, severity, or frequency of conditions present at the start of the study
- Subject deterioration beyond what would be expected due to the primary illness
- Intercurrent illness
- Drug interaction

All suicidal behaviors and clinically significant suicidal ideations will be documented as an AE.

Subjects or parent(s)/caregiver(s) should be questioned in a general way, without asking about the occurrence of any specific symptom. The investigator should attempt to establish a diagnosis of the event based on signs, symptoms, and/or other clinical information. In such cases, the diagnosis should be documented as the AE and not the individual signs/symptoms. Following questioning and evaluation, all AEs, whether believed by the investigator to be related or unrelated to the study treatment, must be documented in the subject's medical records, in accordance with the investigator's normal clinical practice and on the AE eCRF. Each AE is to be evaluated for duration, intensity, frequency, seriousness, outcome, other actions taken, and relationship to the study treatment.

The following are not considered AEs:

- Seizures will not be considered an AE unless there is a significant increase in seizure frequency, a new seizure type, occurrence of status epilepticus, and/or in the investigator's opinion it should be captured as an AE.
- Continuous persistent disease/symptom present before study treatment administration, unless it unexpectedly progresses, or increases in severity following study treatment administration

- Study treatment failure or lack of efficacy
- Pregnancy
- Overdose of either study treatment or concomitant medication without any clinical signs or symptoms

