4.3.5. Handling of Missing Data

4.3.5.1. Start Dates for Adverse Events (AEs)

Missing and incomplete dates for AEs will be imputed for the purpose of estimating the time of the event in relationship to study treatment.

The imputation rules for AE start dates are as follows:

- If the date is completely missing, the date will be imputed as the date of the first dose;
- If only the day is missing, the date will be imputed as the date of the first dose if the month and year of the AE start date match the month and year of the first dose; otherwise, the missing day will be imputed as the first day of the month;
- If both the day and month are missing, the date will be imputed as the date of the first dose if the AE start date is in the same year as the first dose; otherwise, the missing day and month will be imputed as 01 January;
- If any of the above imputations result in a start date that is later than an existing (not imputed) end date for the event, the start date will be imputed as the end date.

There will be no imputation for AE stop dates.

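### The working rule for a treatment-emergent adverse event in SAP 9.2 disagrees with its own definition, the protocol's, or SAP 4.3.5.1 in three narrow cases

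*SAP*

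**What the plan says.** **Definition.** Protocol 10.1: "A treatment-emergent adverse event (TEAE) is an AE that started or worsened in severity following the first dose of study treatment". The first sentence of SAP 9.2 likewise requires that the event was absent before dosing in this study, "or is an already present condition that worsens either in intensity or frequency following the initiation of study drug dosing in CSWS2025".

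**Date test.** The next sentence of SAP 9.2 turns this into a rule: "It is defined by an onset date and time on or after the date of the first dose", with an upper limit of 14 days after the last dose date. It mentions no worsening date.

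**Unknown onset.** SAP 9.2 continues: "If the AE onset date and time are unknown, it will be assumed that the AE is a TEAE". A further sentence treats an AE on the first-dose date with unknown time as a TEAE. The paragraph then refers to Section 4.3.5.1 for missing and partial start dates.

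**Imputation.** SAP 4.3.5.1 sets a completely missing start date to the first-dose date. If an imputed start would fall after a known end date, "the start date will be imputed as the end date".

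**General statement.** SAP 9 says: "Safety data will not be subject to any imputation".

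**The concern.** The definition and the date test should pick out the same events, because the date test is what gets programmed. Here the test looks only at onset and only at the calendar date of the first dose, while the definition also covers worsening and turns on what was present before dosing began. A separate sentence on unknown onset competes with the imputation rule.

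This matters because the rule feeds the primary endpoint (Protocol 11.4.1). There is no hypothesis test (Protocol 11.1), so the descriptive count is the result. Case (a) can drop a serious on-drug worsening. Cases (b) and (c) can add an event that arose before any dose in this study. Two programmers working from different sentences could reach different counts, although SAP 1 says that decisions on the final analysis will be made before database lock and documented in the SAP.

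**Working it through.** The plan gives no figure to reproduce; this is a check of rules against one another.

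**Who can have a pre-dose AE record.** Protocol 10 records AEs from consent for subjects who do not enroll directly, and from Day 1 for those who do. SAP 3 allows screening up to 28 days before dosing. Cases (a) and (b) therefore concern mainly indirect and de novo subjects. Case (c) can occur in anyone: Protocol 9.4.2.1 places vital signs, ECG and laboratory tests on Day 1 before a first dose taken at the site.

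**Test records.** The dates are assumed: first dose 15 March at 09:00, last dose one year later. The definition column uses the first sentence of SAP 9.2, applied to the start date after imputation.

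| Record | Start after 4.3.5.1 | Date test | Unknown-onset sentence | Definition |
|---|---|---|---|---|
| Onset unknown, ended 5 March | 15 March, capped to 5 March | Not TEAE | **TEAE** | Not TEAE |
| Onset unknown, ended 5 April | 15 March | TEAE | TEAE | TEAE |
| Onset unknown, no end date | 15 March | TEAE | TEAE | TEAE |
| Onset in March, day missing, ended 5 March | 15 March, capped to 5 March | Not TEAE | Does not apply | Not TEAE |
| Onset year only, ended 5 February | 15 March, capped to 5 February | Not TEAE | Does not apply | Not TEAE |
| 1 to 5 March, fully dated | 1 March | Not TEAE | Does not apply | Not TEAE |
| Onset 5 March, worsens on drug, same record | 5 March | **Not TEAE** | Does not apply | TEAE |
| Same worsening as a new record, onset 25 March | 25 March | TEAE | Does not apply | TEAE |
| Onset 15 March 07:00, before the 09:00 dose | 15 March | **TEAE** | Does not apply | Not TEAE |

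The bold entries are the only departures, and they are the three cases:

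- Row 1 is case (b). The date test, applied to the capped date, gives the right answer. The unknown-onset sentence gives the opposite one.
- Row 7 is case (a). Row 8 shows that the problem disappears if the site opens a new record for the worsening.
- Row 9 is case (c). The SAP sentence on unknown onset time on the first-dose date would not be needed unless known times were meant to count, but the test as worded does not use them.

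**Size.** Protocol 11.2 gives up to approximately 24 subjects. If all 24 are in the safety set, one subject is 1/24 = 0.0417, or 4.2 percentage points. SAP 9.2 counts unique subjects, so the shift is zero if the event is not serious or if the subject has another serious TEAE.

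**The case against.** - **The end-date cap is the natural exception.** SAP 9.2 points to 4.3.5.1 in the same paragraph, and the unknown-onset sentence agrees with the first imputation rule. A careful programmer would probably apply the cap. A serious event with a known end but no onset date is also unlikely, since onset dates are collected (Protocol 10.2) and SAEs are reported within 24 hours (Protocol 10.4.3). This stands as a limit on how often case (b) matters. It does not supply the missing statement of precedence.
- **Worsening may get its own record.** Protocol 9.3 requires worsening of an existing condition to go on an AE page, Protocol 10.1 lists worsening among AEs, and Protocol 10.2 makes each AE a separate entry. SAP 5.5 puts parent-study AEs ongoing at enrollment into medical history, so they have no earlier AE record in this study. This narrows case (a) but does not remove it. Nothing says that an AE already on a page gets a new record or onset date when it worsens.
- **The Day 1 case covers only the hours before dosing and errs toward inclusion.** True, but it still departs from both definitions.
- **The no-imputation sentence is general, and 4.3.5.1 is specific.** This largely stands; an exemption is tidying.
- **Serious events stay visible.** SAP 9.2 provides a separate SAE listing not limited to TEAEs. So an excluded serious worsening would be listed, though not counted in the primary endpoint.

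**Conclusion.** The rule is wrong as written in the three cases and should be corrected, but its reach is small. The errors run in both directions: (a) removes events, while (b) and (c) add them. The net effect cannot be stated, because the documents do not give the number of affected records. For one reclassified serious event the maximum shift is 4.2 percentage points, assuming 24 subjects in the safety set and no other serious TEAE in that subject.

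A reader might infer more, and the documents do not support it:

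- That the date test itself contradicts the imputation rule. Applied to the imputed date, it excludes events that ended before dosing. The conflict comes from the unknown-onset sentence.
- That events which ended before the first dose generally count as treatment-emergent. Partly and fully dated ones are excluded correctly; only a wholly undated onset with a known pre-dose end is in dispute.
- That every on-drug worsening of a pre-dose condition is lost. That depends on the worsening staying on the existing record.

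**What to change.** Reword SAP 9.2 along these lines:

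> A TEAE is an AE whose onset, after imputation under Section 4.3.5.1 (whose end-date cap takes precedence), is at or after the first dose, using date and time where the time is known and date otherwise; or an AE with earlier onset whose intensity or frequency worsened after the first dose. In either case the onset or worsening must fall no later than 14 days after the last dose.

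Then:

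- Limit the unknown-onset assumption to AEs without a known end date before the first dose.
- Before database lock, identify by data review the pre-dose AEs that worsened, and the date of worsening.
- In SAP 9, exempt AE start-date imputation under 4.3.5.1 from the no-imputation sentence.
- Do not add seriousness as a worsening criterion. The SAP uses intensity or frequency, the protocol uses severity, and Protocol 10.1.1 separates severe from serious.

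The cost is SAP wording, one programming step and the data-review check. Protocol 10.2 lists onset and resolution dates but no worsening date, so the review may need queries to sites for the few records concerned.

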9.4. Neurological, [REDACTED] Examinations

Frequency tables (ie, number and percentage of subjects) will be presented categorically by visit for neurological examinations including consciousness, mental status, muscle strength and tone, coordination, and gait; as well as for [REDACTED]

Neurocrine Biosciences, Inc.
Statistical Analysis Plan

Study NBI-827104-CSWS2025
6 September 2024

